#### 7. STUDY CONDUCT

**Table 1. Schedule of Events** 

Visit	Visit 1 Screening^ Day -28 to Day -1	Visit 2, Day 0 Baseline/ Randomization	Visit 3/ Week 1 Day 7 (+2)	Visit 4 (End of the study)/ Week 2 Day 14 (+2)
Consent	X			
Weight and height	X			
Vitals	X	X	X	X
Medical history	X			
Concomitant medication	X	X	X	X
Physical examination \$	X			X
12-lead ECG	X			
Chest X-ray#	X			
Colonoscopy*	X			
Pregnancy test (female patients of child bearing potential)	X (Serum)	X (Urine)	X (Urine)	X (Urine)
Haematology/Biochemistry/Uri ne analysis\$	X			X
Inclusion/exclusion criteria	X			
Inclusion and Exclusion criteria Verification		X		
Randomization		X		
Study Drug Dispensing		X	X	
Study Drug return and accountability check			X	X
Subject Diary Dispensing	$X^a$	X	X	
Subject Diary collection and Review		X	X	X
SBM Assessment	X	X	X	X
Assessment of CSBM, Stool consistency, Degree of Straining, Abdominal bloating, Abdominal discomfort	x	x	x	x
Adverse events recording	X	X	X	X

^This study includes a 2-week pre-treatment period (day -14 to -1) between screening and randomization to assess the study eligibility and baseline SBM frequency. *Patients reporting more than 3 SBM during pretreatment period will be excluded from the study*.

\$Lab assessments including Haematology/Biochemistry/Urine analysis will be conducted after completion of 14 day wash out period. This will be considered as part of the screening visit.

If the patient meets the entry criteria assessed at the Screening Visit and does not require a washout of prohibited medicines, then patient can be randomized after completion of 2 weeks pretreatment period and diary and rescue medications can be provided on the same day

\$ Physical examination includes Cardiovascular, Nervous, Gastrointestinal, Respiratory system and any other specific examination, as per the investigator's discretion.

#X-ray done in past 3 months of screening will be valid;

\*Colonoscopy reports of within two years period from screening time are valid; Colonoscopy can be avoided for patients age less than 45 years and those who do not have alarming symptoms of weight loss, rectal bleeding or anemia in past 6 months based on Investigator discretion/ Medical Monitor opinion (Rectal examination to be performed during the screening period on all patients who do not require a colonoscopy). SBM: Spontaneous Bowel Movement; CSBM: Complete Spontaneous Bowel Movement; If the patient meets the entry criteria assessed at Screening and requires a washout period according to prohibited medicine section as per protocol, below mentioned points should be followed:

<sup>a Diary entry should start after the completion of wash out period:

## 7.1. Study Procedures

## 7.1.1. Visit 1 (Screening/ Day -28 to -1)

At the Screening Visit, a review of inclusion and exclusion criteria will be conducted to determine the patient's eligibility for progression to the pretreatment period. Trial procedures will be reviewed with the patient, the caregiver, and/or the legally authorized representative (if different from the caregiver); and documentation of informed consent will be obtained. After the patient signs the ICF, the Trial Coordinator will register the patient for the screening period, and the patient will then be assigned a unique PID number in sequential order. The following procedures will be performed thereafter:

- Recording of medical history
- Performance of physical examination (Cardiovascular, Nervous, Gastrointestinal, Respiratory system and any other specific examination, as per the investigator's discretion).
- Measurement of body weight and height
- Recording of vital signs (temperature, respiratory rate, systolic and diastolic blood pressure, and pulse rate)
- Chest X-ray#
  - \*X-ray done in past 3 months of screening will be valid
- 12-lead ECG
- Rectal examination should be performed during the screening period on all patients who do not require a colonoscopy. Colonoscopy can be avoided for patients age less than 45 years and those who do not have alarming symptoms of weight loss, rectal bleeding or anemia in past 6 months based on Investigator discretion/ Medical Monitor opinion. In subsequent visits, the rectal examination may be performed at the discretion of the Investigator
- Documentation of prior and concomitant medicines
- Collection of blood and urine samples for clinical laboratory determinations\* (Refer table
   2 for details of laboratory investigations)
  - \*if the patients are required to undergo 14 days wash out period then these investigations to be conducted after completion of wash out period.
- Adverse event (AE) assessment
- Providing instructions for washout period, if required
- Review of inclusion and exclusion criteria
- Diary training and dispensing of rescue medication#

#if the patients are required to undergo 14 days wash out period then these activities to be conducted after completion of wash out period

- Providing all applicable instructions to the patients regarding pretreatment period
- Two weeks pretreatment period (day -14 to -1) is in between screening and randomization
- The purpose of this pretreatment period is to collect information regarding bowel habits of patients through patient diaries and to determine whether the patient is eligible to continue into the treatment period of the trial.

## 7.1.2. Visit 2 (Randomization visit/ Day 0)

The following procedures will be performed before randomization and administration of the first dose of study drug at the trial center:

- Recording of vital signs (temperature, respiratory rate, systolic and diastolic blood pressure, and pulse rate)
- Diary Collection and review of Patient Diary to assess:
  - o Number of Spontaneous Bowel Movements
  - Sensation of complete evacuation
  - Stool consistency
  - Severity of straining
  - Abdominal Bloating Score
  - Abdominal Discomfort Score
  - Complete Spontaneous Bowel Movements
  - Use of per-protocol rescue medicine
- Urine pregnancy test for females of childbearing potential
- Review of adverse events (AEs)
- Verification of inclusion and exclusion criteria
- Documentation of concomitant medicines used if any
- Allocation of the treatment as per randomization
- Dispensing of study drug
- Dispensing of rescue medication (if required)
- Issue of subject Diary with instructions

## 7.1.3. Visit 3: Week 1/Day 7 (+2)

The following procedures will be performed:

• Vital signs

Diary Collection and review of Patient Diary for:

- Number of Spontaneous Bowel Movements
- o Sensation of complete evacuation
- Stool consistency
- Severity of straining
- o Abdominal Bloating Score
- Abdominal Discomfort Score
- o Complete Spontaneous Bowel Movements
- o Use of per-protocol rescue medicine
- Urine pregnancy test for females of childbearing potential
- Review of adverse events (AEs)
- Documentation of concomitant medicines used if any
- Study drug return and accountability check
- Dispensing of study drug
- Dispensing of rescue medication (if required)
- Issue of subject Diary with instructions

# 7.1.4. Visit 4: Week 2/Day 14 (+2)/ End of Treatment Visit:

Any clinical findings obtained during the final examination or at premature discontinuation for any reason, including clinically significant laboratory abnormalities, will be followed until the condition returns to screening status, has resolved or stabilized, or can be explained as being unrelated to study drug.

Patients who complete the Treatment Period will undergo the following procedures:

- Physical examination
- Vital signs
- 12-Lead ECG

Diary Collection and review of Patient Diary for:

- Number of Spontaneous Bowel Movements
- Sensation of complete evacuation
- Stool consistency

- Severity of straining
- Abdominal Bloating Score
- o Abdominal Discomfort Score
- o Complete Spontaneous Bowel Movements
- o Use of per-protocol rescue medicine
- Urine pregnancy test for females of childbearing potential
- Review of adverse events (AEs)
- Documentation of concomitant medicines used if any
- Study drug return and accountability check
- Return of rescue medication
- Collection of blood and urine samples for clinical laboratory determinations. Refer table for details of laboratory investigations.

# **Clinical Laboratory Determination:**

At the Screening Visit (Visit 1) and End-of-Trial visit, the Investigator will assess clinical significance of any values outside the reference ranges.

The following clinical laboratory tests will be performed:

Table 2: Clinical Laboratory Tests

Hematology		Biochemistry	Urinalysis		
Hemoglobin (Hb %)	•	RBS	Colour		
• Total and Differential	•	Renal Function Test:	Transparency		
WBC count		Blood urea nitrogen, Creatinine	рН		
• Platelet count	•	Liver Function Test	Specific gravity		
• RBC count		Total Protein, S. albumin,	Protein		
Absolute Neutrophil		Total and direct bilirubin, ALT,	Glucose		
Count		AST, Alkaline phosphatase	Ketone bodies		
	•	Serum electrolytes:	Bilirubin		
		Sodium, Potassium and chloride	Blood		
			Nitrite		
			Urobilinogen		
			Microscopic examination		
			WBC, RBC, Casts, Crystals		
Serum Pregnancy test #					
• Urine Pregnancy Test (UPT)*					
*Serum pregnancy test will be performed at screening visit/Visit 1					
* Urine pregnancy will be p	* Urine pregnancy will be performed at every subsequent visit after screening visit				

ALT=alanine transaminase, AST=aspartate aminotransferase, RBC=red blood cell, RBS=random blood sugar, WBC=white blood cells

## 7.2. Early Termination of the Study

Sponsor reserves right to discontinue the study at any time. Principal Investigator reserves the right to discontinue the study for safety reasons at any time. Independent / Institutional Ethics Committee (IEC) may ask to terminate the study, if there are major violations of ethical considerations or due to any serious adverse event(s). Reason(s) for termination of study will be provided to the subjects.

If a subject experiences any AE/SAE or worsening of the existing condition he/she can visit the site for an unscheduled visit. Subjects who withdraw from the study will be requested to attend an early termination visit, where Visit 4 (end of trial visit) procedures will be performed.

# 7.3. Withdrawals and Dropouts

Please refer the section 5.3 (Withdrawal Criteria) of the protocol for details of withdrawal criteria.

#### 7.4. Protocol compliance and Protocol deviation

The study shall be conducted in compliance with the protocol agreed to by the sponsor and as per approval by the regulatory authority(ies) and which was given approval/favourable opinion by the IEC.

The investigator should not implement any deviation from, or changes of the protocol without agreement by the sponsor and prior review and documented approval/favourable opinion from the IEC of an amendment, except where necessary to eliminate an immediate hazard(s) to study subjects.

While deviations from the protocol should be avoided, if deviations do occur, the investigator/site staff must inform the sponsor monitor and the implications of deviations will be reviewed and discussed. Deviations will be documented and explained with reasons, date(s) of occurrence, and actions taken. All the deviation should be notified to respective ethics committee.

## 7.5. Audits and inspections

Any aspect of the clinical trial may be subject to audits conducted by Sponsor Quality assurance team or inspections from national or international regulatory authorities or from IRBs/IECs. The purpose of a sponsor's audit, which is independent of and separate from routine monitoring or quality control functions, is to evaluate trial conduct and compliance with the protocol, SOPs, GCP, and the applicable regulatory requirements.

#### 8. STUDY TREATMENT

#### 8.1. Study Drug

## Test drug:

Elobixibat tablet (10 mg oral once daily self-administered as two tablets of 5 mg) before Breakfast from Day 1.

## **Comparator:**

Matching placebo (10 mg) self-administered oral once daily as two tablets before breakfast from Day 1.

#### 8.2. Administration

- The usual adult dosage is 10 mg of elobixibat self-administered orally once daily before breakfast from day 1. The dose may be adjusted according to the patient's symptoms, but the maximum daily dose will be 15 mg.
- Since abdominal pain and diarrhea may occur during administration of this drug, it is
  necessary to consider reducing the dose, suspending or discontinuing the drug
  depending on the symptoms, and to continue administration of this drug on a regular
  basis so as not to continue administration of this drug indiscriminately.

# 8.3. Storage Requirements

All study drug supplies will be stored as per COA or as per sponsor's / manufacturer's instructions. Until dispensed to the subjects, the study drug will be stored in a secure, temperature controlled, restricted access area accessible to authorized personnel only

#### 8.4. Concomitant treatment

• Prohibited Medication:

Prescription and over-the-counter (OTC) laxatives other than those prescribed as a rescue medication during the baseline/washout period by the Investigator.

Note: the use of fiber, bulk laxatives, stool softeners [surfactants such as docusate], and probiotics are acceptable, provided that the patient has been on a stable dose for 30 days before the Screening Visit and plans to continue stable dosing for the duration of the trial.

- Significant change in diet.
- Over-the-counter or prescription laxatives cannot be administered during the pretreatment period(s).

All medicine listed below ("1-day Washout" and "14-day Washout") are excluded during the Pretreatment and Treatment Periods.

- A 1-day washout means that the particular medicine is not allowed during the calendar day before the Pretreatment Visit
- A 14-day washout means that the particular medicine is not allowed during the 14 calendar days before the Pretreatment Visit

1-Day Washout (no medicine during the calendar day before the Pretreatment Visit)

- 1. Any over-the-counter or prescription laxative, suppository, or enema (e.g., polyethylene glycol, lactulose, Fleet's) and any herbal or natural agent that a person might take for constipation. Note: The use of fiber, bulk laxatives, stool softeners (surfactants such as docusate), and probiotics is acceptable, provided the patient has been on a stable dose during the 30 days before the Screening Visit and plans to continue stable dosing throughout the trial.
- 2. Any medicine used to treat diarrhea (e.g., bismuth subsalicylate, kaolin)
- 3. NSAIDs if taken for abdominal pain or discomfort.
- 4. Others: Midazolam, Aluminum containing antacid.
- 14-Day Washout (no medicine during the 14 calendar days before the Pretreatment Visit)
- 1. Drugs with known pharmacological activity at 5-HT4, 5-HT2b or 5-HT3 receptors (e.g., cisapride, tegaserod, ondansetron, tropisetron, granisetron, dolasetron, and mirtazapine).
- 2. Any treatment specifically taken for IBS-C or CIC alone or in combination, including lubiprostone, an approved chloride channel activator that enhances intestinal fluid secretion, linaclotide, plecanatide, colchicine, and misoprostol. Note: patient has taken commercially available elobixibat, linaclotide or participated in a linaclotide or plecanatide or elobixibat clinical study during the 30 days before the Screening Visit.
- 3. Prokinetic agents (e.g., metoclopramide, itopride, prucalopride, and domperidone).
- 4. Anti-cholinergic agents (e.g., dicyclomine, flavoxate, scopolamine, hyoscyamine, propantheline, oxybutynin, tolterodine, solefenacin, darifenacin, and trospium). Note: inhaled ipratropium and tiotropium are permitted.
- 5. Bile acid sequestrants (e.g., cholestyramine and colestipol).

- 6. Cholinomimetic agents (e.g., bethanechol, pyridostigmine, tacrine, and physostigmine). Note: intraocular cholinomimetic agents (e.g., pilocarpine) are permitted.
- 7. Antipsychotic agents (e.g., risperidone, haloperidol, droperidol, chlorpromazine, perphenazine, all phenothiazines, quetiapine, olanzapine, and clozapine) unless the patient has been on a stable dose for 30 days before the Screening Visit and there is no plan to change the dose after the Screening Visit. Note: paliperidone is permitted without restriction.
- 8. Antidepressants unless the patient has been on a stable dose for 30 days before the Screening Visit and there is no plan to change the dose after the Screening Visit. Specifically included are the following: Tricyclic antidepressants (e.g., amitriptyline, imipramine, and nortriptyline); Monoamine oxidase inhibitors (e.g., furazolidone, isocarboxazid, pargyline, phenelzine, and selegiline tranylcypromine); Selective serotonin reuptake inhibitors (e.g., fluoxetine, sertraline, paroxetine, and citalopram); Serotonin and norepinephrine reuptake inhibitors (e.g., venlafaxine and desvenlafaxine succinate) Others (e.g., trazodone, and bupropion).
- 9. Calcium channel blocker verapamil unless the patient has been on a stable dose for 30 days before the Screening Visit and there is no plan to change the dose after the Screening Visit. Note: all other calcium channel blockers (e.g., nifedipine, diltiazem, amlodipine, felodipine, nicardipine, nimodipine, nisoldipine, etc.) are permitted and may be used without restriction.
- 10. Oral and parenteral antibiotics (However, a standard regimen [up to 10 days] of oral antibiotics is permitted.).
- 11. Any investigational or imported drugs that have not been approved for human use by the US FDA.
- 12. All narcotics either alone or in combination (e.g., tramadol, codeine, morphine, propoxyphene, loperamide, diphenoxylate, and paregoric). Note: narcotics used as anesthesia for a colonoscopy require a 5 calendar day wash-out prior to the patient entering into the Pretreatment Period.
- 13. Any medicine taken for the purpose of losing weight (e.g., orlistat, phentermine, phendimetrazine, diethylpropion, benzphetamine, and sibutramine).
- 14. Any medicine that is known to cause diarrhea (e.g., acarbose).

15. Proton pump inhibitors (e.g., omeprazole, lansoprazole, esomeprazole, pantoprazole, rabeprazole) unless the patient has been on a stable dose for 30 days before the Screening Visit and there is no plan to change the dose after the Screening Visit.

16. Others: barbiturates (e.g., butalbital and phenobarbital) and chronic oral or parenteral glucocorticoids (which must be discontinued at least three months before screening; however, one 10-day course of oral or 1 injection of parenteral glucocorticoids is permitted), Ursodeoxycholic acid, chenodeoxycholic acid, Sucralfate hydrate, aldioxa, etc. Cholestyramine, Digoxin, dabigatran etexilate, and methane sulphonate. Pregabalin, is acceptable, provided the patient has been on a stable dose during the 30 days before the Screening Visit and plans to continue stable dosing throughout the trial.

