# 2 weeks pretreatment period (Day -14 to Day -1) between screening and randomization

Visit 2 (Randomization visit, Day 0)

Visit 3: Week 1/ Day 7 (+2)

Visit 4: Week 2/Day 14 (+2)

Treatment	Drug Administered	No of
Group		Subjects
Intervention/Test Product	Elobixibat 5 mg tablet.*	75
Comparator	Placebo (Matching placebo oral once daily as two tablets)	75

\* Elobixibat tablet (10 mg oral once daily self-administered as two tablets of 5 mg) in patients with chronic constipation once daily for one week and then dose titration (up or down) will be done according to the patient's response.

The trial consists of three distinct periods defined as follows:

1. The screening period starts with signature of the ICF and lasts for up to 28 calendar days. During this period, patient eligibility for entry into the pretreatment period will be determined. This study includes a 2-week pre-treatment period (day -14 to -1) between screening and randomization to assess the study eligibility and baseline SBM frequency. Assessment of prohibited medications is conducted at the time of screening and accordingly if the patient meets the entry criteria assessed at the Screening Visit and does not require a washout period then patient can directly enter the pretreatment period of 14 days after screening. If the patient requires a washout period, then pretreatment period is started after the completion of wash out period. Any over-the-counter or prescription laxatives, suppositories, or enemas used to treat Chronic Constipation must not be taken during the calendar day before the start of Pretreatment period; whereas other prohibited medicines must not be taken during the 14 calendar days before the start of Pretreatment period. *The pretreatment period* is defined as the 14 calendar days immediately before randomization.

**Note:** Patients reporting more than 3 SBM during pretreatment period will be excluded from the study.

- 2. **The treatment period** begins with randomization and lasts for 2 weeks. Patients who meet all entry criteria will be randomized to treatment with 5\*mcg Elobixibat, or placebo (1:1).
- \* Elobixibat tablet (10 mg oral once daily self-administered as two tablets of 5 mg) in patients with chronic constipation once daily for one week and then dose titration (up or down) will be done according to the patient's response.

Patient will be advised to take study drug once daily in the morning before breakfast from Day 1.

[figure not shown]

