- 19. Has a history of hospitalization for any psychiatric disorder, or any suicide attempt in the 2 years prior to Screening
- 20. History of alcohol or drug abuse during the 6 months prior to Screening
- 21. Reported using a Prohibited Medicine (excluding laxatives, suppositories, and enemas) during the Pretreatment Period or was not willing or able to abide by the restrictions regarding use of Prohibited Medicines (Note: The use of fiber, bulk laxatives, or stool softeners [such as docusate] was acceptable provided the patient had been on a stable dose during the 30 days before the Screening Visit and planned to continue on a stable dose throughout the trial).
- 22. Patients having following lab parameters deranged defined as follows:
  - **Renal function:** Serum Creatinine  $\geq 1.5 \times$  upper limit of normal (ULN)
  - **Hepatic function:** AST and ALT  $\ge 3 \times ULN$ ;
  - **Hemoglobin:** < 8g/dL
- 23. Has a clinically significant laboratory finding or medical condition that could potentially affect study participation and/or personal well-being, as judged by the investigator.

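### Section 8.4 item 16 handles digoxin and dabigatran by washout, so a willing established user could be off a cardiac drug or anticoagulant for about 42 days; excluding such patients at screening would be safer

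*Protocol*

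**What the plan says.** Protocol section 8.4 has a 1-day and a 14-day washout list. Item 16 of the 14-day list collects other medicines. It opens with barbiturates (butalbital and phenobarbital are the examples) and chronic glucocorticoids, and later names "Cholestyramine, Digoxin, dabigatran etexilate, and methane sulphonate". The last entry looks like the salt name of dabigatran, which section 1.2 gives as one term. Medicines on both lists "are excluded during the Pretreatment and Treatment Periods".

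Needing a washout does not make a patient ineligible. Section 4.1 says: "If the patient requires a washout period, then pretreatment period is started after the completion of wash out period". The footnotes to Table 1 open the same route with "If the patient meets the entry criteria assessed at Screening and requires a washout period according to prohibited medicine section as per protocol", and section 7.1.1 has washout instructions given at screening where required.

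Three general provisions bear on who may take that route. Exclusion 21 in section 5.2 removes a patient who used a prohibited medicine (other than laxatives, suppositories and enemas) during pretreatment or who "was not willing or able to abide by the restrictions regarding use of Prohibited Medicines". Exclusion 23 covers a clinically significant laboratory finding or medical condition that the investigator judges could affect participation or well-being. Section 15 makes a qualified physician responsible for medical decisions in the trial.

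Section 1.2 gives the reason for concern about digoxin and dabigatran: elobixibat inhibits P-glycoprotein, so their blood levels may rise. This appears under precautions for combined use. Neither drug is among the contraindications.

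**The concern.** Barring a medicine alongside study drug is one decision. How to treat a patient who already depends on it is another. For the second, the written procedure is washout. Digoxin and dabigatran are a cardiac drug and an anticoagulant, and phenobarbital raises the same kind of question. The trial treats constipation for two weeks, and a patient could be taken off one of these medicines to qualify.

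No exclusion in section 5.2 names established users of these medicines, or the cardiac, thromboembolic or seizure conditions for which they might be taken. Nothing in sections 4.1, 7.1.1 or 8.4 asks for a check of medical need, the prescriber's agreement or a substitute before washout begins. With 10 to 15 centres planned (section 5.5), the decision is left to each site and may differ between them. What is at stake is the safety of a small number of participants.

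**Working it through.** **Inputs**

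- Washout: 14 calendar days before the pretreatment visit (section 8.4).
- Pretreatment: the 14 calendar days immediately before randomization (section 4.1).
- Treatment: 2 weeks from randomization, final visit at Day 14 with a window of +2 days (section 4.1).
- Screening period: up to 28 calendar days (section 4.1).

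**The plan's own figure.** Washout plus pretreatment = 14 + 14 = 28 days. This equals the stated maximum for screening, so a full washout followed by pretreatment fits the schedule exactly.

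**Time off the medicine for a patient who washes out and completes**

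- Before any study drug: 14 + 14 = 28 days.
- To the end of treatment: 28 + 14 = 42 days.
- With the full Visit 4 window: 42 + 2 = 44 days.
- Counting Day 0 as a separate day adds one, giving 43 to 45.

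About two thirds of the time off the medicine (28/42) therefore falls before any dose of study drug.

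**Can a willing established user get through the criteria?**

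1. At screening the patient takes digoxin or dabigatran. No exclusion names this.
2. The patient agrees to stop. The first half of the compliance wording in exclusion 21, on willingness, is met.
3. The second half asks whether the patient is able to comply. The text does not say whether this means medically able. An investigator may read it so, but need not.
4. Exclusion 23 depends on the investigator's judgement about a finding or condition. It does not mention need for a prohibited medicine.
5. After 14 days off the medicine, pretreatment begins. If the patient stays off it, the pretreatment-use limb of exclusion 21 does not apply, and the patient can be randomized.

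Entry is therefore permitted. It is not required, and an investigator can refuse at steps 3 or 4.

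**Barbiturates.** In item 16 the parenthesis requiring discontinuation at least three months before screening follows both barbiturates and chronic glucocorticoids. If it governs glucocorticoids only, a barbiturate user is in the 42-day position above. If it governs both, a current barbiturate user could not enter by the 14-day washout, and anyone who did enter would have been off the drug for longer. The text does not settle which reading is meant.

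**The case against.** The strongest reply is that the safeguard already exists and acts before washout. The Table 1 footnote allows washout only for a patient who already meets the entry criteria assessed at screening, so exclusions 21 and 23 apply first. On an ordinary reading, a patient who medically needs an anticoagulant is not able to do without it. Section 5.3 allows withdrawal where continuing would harm the patient. The appended Declaration of Helsinki (paragraph 14) requires good reason to believe that participation will not adversely affect the patient's health. Leaving individual medical decisions to a qualified physician is normal practice.

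Much of this stands. A careful investigator would probably refuse such a patient, and the protocol gives grounds for doing so. But none of these provisions says that medical need disqualifies, while the specific instruction for a listed medicine is to wash it out. Section 9.6 records adverse events from consent, so an event after stopping should be captured, but that does not prevent it.

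A reader might also infer an inconsistency from the stable-dose exceptions elsewhere on the list, such as "Calcium channel blocker verapamil unless the patient has been on a stable dose for 30 days before the Screening Visit" or, within item 16 itself, "Pregabalin, is acceptable, provided the patient has been on a stable dose during the 30 days before the Screening Visit". The documents do not support that step. Five of the 16 items carry such an exception (7, 8, 9, 15, and 16 for pregabalin only), so eleven carry none. For digoxin and dabigatran, a stable earlier dose would not remove the P-glycoprotein concern in section 1.2. Withholding an exception is defensible.

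**Conclusion.** The point holds as a low-severity safety improvement. As written, the protocol permits a willing established user of digoxin or dabigatran to be off it for about 42 days (44 with the visit window), 28 of them before study drug, with only general wording as a guard. For barbiturates this holds only if the three-month clause does not reach them.

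Three stronger readings should be resisted. The protocol does not require anyone to stop a needed medicine: an unwilling or unable patient is excluded. The prohibition is not itself an error: section 1.2 supports it for digoxin and dabigatran, and applying the bar in both periods keeps baseline and treatment conditions alike. The primary result is not affected.

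The 42 days assume a full 14-day washout and completion of the trial. They measure permitted time off the medicine and say nothing about how often harm would follow. The protocol does not say how many patients aged 18 to 65 would be affected; the number is probably small.

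**What to change.** 1. Add to section 5.2 an exclusion for patients on established treatment with digoxin, dabigatran or a barbiturate at screening, in place of washout for these patients.
2. Keep these medicines prohibited in both pretreatment and treatment. Do not add a stable-dose exception.
3. State in section 8.4 that no medically necessary prescribed medicine may be stopped in order to qualify. This also covers other listed medicines without an exception, such as pyridostigmine in item 6 ("Cholinomimetic agents (e.g., bethanechol, pyridostigmine, tacrine, and physostigmine").
4. Reword item 16 so that it is clear whether the three-month clause applies to barbiturates or to glucocorticoids only.

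The cost is one exclusion line, one sentence and a small rewording, with a few fewer eligible patients. The design, endpoints and sample size are unchanged.
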